***Inclusion criteria:***

- **Aged  $\geq 50$  years,**
- **Sedentary lifestyle,** defined by self-reported physical activity that breaks a sweat  $<3$  days/week, with no regular resistance exercise for 3 months preceding study,
- **Fatigued** ( $\geq 2.0$  on either of the first two screening items on the *HIV-Related Fatigue Scale*), 

- **Thyroid Stimulating Hormone (TSH)** within normal lab limits,
- **Prescribed HIV antiretroviral therapy** for  $\geq 12$  months, with no current use (within 1 year) of older drugs with established mitochondrial toxicity (i.e., D4T, DDI, ZDV),
- **HIV-1 RNA level  $< 200$  copies/mL**, for a minimum of 12 months prior to enrollment, with an allowed blip to 500 copies/mL presuming repeat assessments are below 200 copies,
- **Willing to participate** in either assigned arm of a 16-week supervised exercise intervention 3 times weekly,
- **Ability to receive messages** from cell phone or email in order to participate in the biobehavioral maintenance intervention,
- **Ability and willingness of participant to provide informed consent** and consent for access to medical record,
- **Completed COVID-19 vaccination and appropriate COVID-19 boosters**

These inclusion criteria are designed to identify a representative group of older adults living with HIV who experience a variety of physical function limitations and symptoms and may benefit from our proposed intervention. Participants are not eligible if they meet any *exclusion criteria*:

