#### Exclusion criteria:

- **Weight over 450 pounds** (due to limitations of the DXA machine)
- **Use of sex hormone therapy**, if on for  $\leq 3$  months (stable doses for  $>3$  months will be permitted)
- **Use of other hormone replacement**, if on for  $\leq 3$  months (stable doses  $>3$  months will be permitted)
- **Anemia** (Hemoglobin  $\leq 9$  g/dL for women or  $\leq 10$  g/dL for men) due to contribution to fatigue,
- Diagnosis of **mitochondrial disease**,
- For participants undergoing the muscle biopsy only, use of anticoagulant therapy other than low dose aspirin that cannot be held for at least 7 days for the muscle biopsy. Aspirin and non-steroidal use will be permitted but will be held for 7 days prior to the muscle biopsy, and can be resumed following the biopsy.
- For the MRI/MRS optional imaging: participants with implanted devices (i.e. pacemaker or insulin pumps), have severe claustrophobia, and females who are pregnant will be excluded.
- Due to the expected fatigue associated with COVID-19 and potential infection risk, anyone with a diagnosis of COVID will not be eligible for enrollment until at least 30 days after symptom resolution and return to baseline level of function.
- **Active substance abuse** or other factors that could prevent compliance or safety with study visits, at the discretion of the site investigator,
- Reasons for **medical exclusion**, as determined by [name] or a provider at the University of Washington:
  - **Uncontrolled hypertension** defined as resting systolic blood pressure  $>150$  mmHg or diastolic blood pressure  $>90$  mmHg; participants who do not meet these criteria at first screening will be re-evaluated, including follow-up evaluation by their primary care provider with initiation or adjustment of anti-hypertensive medications,
  - **Unstable ischemic heart disease** (e.g., angina, ST segment depression) or **serious arrhythmias** at rest or during the graded exercise test without negative follow-up evaluation will be cause for exclusion; follow-up evaluation must include diagnostic testing (e.g., thallium stress test) with interpretation by a cardiologist,
  - **New York Heart Association Class III or IV congestive heart failure**, clinically significant aortic stenosis, uncontrolled angina, or uncontrolled arrhythmia,
  - **Pulmonary disease** requiring the use of supplemental oxygen at rest or with physical exertion,

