### **C. Study Design and Research Methods**

**Aim 1. Compare the effects of HIIT and CME on physical function (1°) and fatigue (2°) in older PWH.**

**Procedures/Outcome Measures (Table 3)**

|  | Baseline (up to 8 weeks) |    |                       |    | Week of HIIT vs CME (Aim 1) |   |   |   |    | End of Part 1 Visit (can overlap with week 16 visits)
Coach vs Control |   | (Aim 3) |   |   |    | End of Primary Study | End of Cognitive Substudy |
|--|--------------------------|----|-----------------------|----|-----------------------------|---|---|---|----|---|---|---------|---|---|----|----------------------|---------------------------|
|  | #1                       | #2 | #3                    | #4 | 0                           | 2 | 4 | 8 | 12 | 16  |   | 0       | 4 | 8 | 12 | 28                   | 48                        |
| Consent                                | X                        |    |                       |    |                             |   |   |   |    |   |   |         |   |   |    |                      |                           |
| Medical History                        | X                        |    |                       |    |                             |   |   |   |    |   |   |         |   |   |    |                      |                           |
| Physical exam                          | X                        |    |                       |    |                             |   |   |   |    |   |   |         |   |   |    |                      |                           |
| VO 2 peak                   | X                        |    |                       |    |                             |   |   |   |    | (or X)  | X (not on same day of physical function or muscle biopsy) |         |   |   |    |                      |                           |
| MRI Scan                               |                          |    |                       | X  |                             |   |   |   |    |   | X   |         |   |   |    |                      |                           |
| Urine Pregnancy Test (if menstruating) |                          |    | X (prior to DXA scan) |    |                             |   |   |   |    | X (prior to DXA scan)   |   |         |   |   |    |                      |                           |

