**Risks:** The DXA (for measures of body composition) involves exposure to ionizing radiation. The DXA scans (total body,) at 2 times during the study involve a total effective radiation exposure of about 60 mrem. DXA involves  $< 3\%$  of the annual maximum non-therapeutic radiation exposure to the whole body recommended by the FDA (5000 mrem/year). Urine pregnancy will not be performed prior to DXA scans, as all women will be post- childbearing state (ie, post-menopausal).

**Plans to minimize risk:** The risk of radiation exposure is minimized by having trained technicians administer the DXA, thereby reducing the likelihood of needing repeat assessments.

Justification: DXA is a routine test obtained in clinical practice and will provide important data regarding the impact of exercise on lean and fat mass.

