### **Neuroimaging (MRI) UAB ONLY:**

**Risks:** People with claustrophobia may be uncomfortable in the scanner. The MRI machine may also be loud and cause discomfort. MRI is not safe for people with certain conditions such as pregnancy or implanted metal in the body.

**Plans to minimize risk:** We will carefully screen participants prior to doing the MRI to ensure the procedure is safe for them. Specifically, we will exclude those with claustrophobia, those who are pregnant (confirmed via pregnancy test on site), and those who have any implanted devices (e.g., pacemaker, insulin pumps), or embedded metal in the body (dental work is OK). Participants will also be provided with ear plugs to help increase comfort. Not being able to do the MRI will not affect participation in the other parts of the study, and the participant will be compensated if they attempt the MRI but cannot finish.

**Justification:** As this is an exploratory aim, we have elected to conduct the neuroMRI at only 2 time points at only one site of this study, under the supervision of a Co-I who is an expert in this technique. The potential risks are unlikely to occur, as we screen for these risk factors and will not scan those with these risk factors. The scientific justification is that understanding the underlying brain impacts of two different types of exercise is significant as it will allow for developing the most effective interventions to prevent or reverse cognitive impairment.

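### The schedule calls for a pregnancy test before DXA in menstruating women, but the DXA risk text rules it out on a premise that no entry criterion secures

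*Combined protocol and SAP*

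**What the plan says.** Three parts of the combined protocol and SAP bear on this point.

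- **Section D, DXA, Risks.** After describing the radiation dose, the text says "Urine pregnancy will not be performed prior to DXA scans", with the reason "as all women will be post- childbearing state (ie, post-menopausal". The plan to minimize risk that follows relies on trained technicians, so that fewer scans need repeating. It names no other safeguard.
- **Section C, Table 3.** The schedule has a row headed "Urine Pregnancy Test (if menstruating"), and its cells read "X (prior to DXA scan"). They stand under baseline visit 3 and week 16, the visits at which DXA is planned.
- **Section B, eligibility.** The only inclusion criterion close to menopausal status is "Aged $\geq 50$ years". Pregnancy appears once in the exclusion list, in the item on optional MRI/MRS imaging: "females who are pregnant will be excluded". Nothing excludes pregnant women from DXA or from the study as a whole.

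**The concern.** Staff preparing a DXA visit cannot follow both texts for a woman who is still menstruating. The schedule tells them to test her. The risk section tells them not to, because it assumes she does not exist. That section is also where an ethics board or a site would look for the rule on radiation safety, and its assurance about all women is stated as fact.

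What is at stake is an avoidable radiation exposure in an unrecognized pregnancy, and a protocol deviation whichever instruction is followed. The efficacy conclusions are not at stake.

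**Working it through.** The plan states no figure that needs reproducing. The check is a comparison of texts, followed by a simple count of who could be affected.

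**1. Do the two instructions conflict?**

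| Woman presenting for DXA | Table 3 | Section D, DXA risks |
|---|---|---|
| Post-menopausal | No test | No test |
| Still menstruating | Test before the scan | No test |

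They agree in the first row and contradict each other in the second. Both are current text, and the document gives no order of precedence between them.

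**2. Can the second row occur?** It cannot if the design guarantees that all women are post-menopausal.

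- The inclusion and exclusion criteria contain no menopausal or sterility condition. Age 50 or over makes menopause likely but does not ensure it.
- FSH is in the blood draw at baseline visit 2, but no threshold is given and it plays no part in eligibility or in deciding on a test.
- The condition attached to the Table 3 row itself allows for menstruating participants.
- The MRI/MRS exclusion for pregnancy applies to a substudy that section B offers at Colorado and Washington, the sites that do DXA. At those sites the protocol therefore does not treat pregnancy as impossible.
- The UAB neuroimaging text excludes "those who are pregnant (confirmed via pregnancy test on site"). This shows the same attitude to the trial population, but UAB does no DXA, so it carries little weight here.

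The second row can occur.

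**3. How many women could be affected?** Inputs: DXA is marked for UW/UCD only (Study Measures by Site, section C). Sixty participants per site begin the intervention and 50 complete it, with a goal of 25% women (section B table).

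- Women beginning the intervention: 2 × 60 × 0.25 = 30.
- Women completing it, and so expected to have the second scan: 2 × 50 × 0.25 = 25.
- Baseline DXA is at visit 3 and randomization comes at the end of that visit, so a few more women than 30 could have a baseline scan.
- Share still menstruating: not given. Taken as anything from 0 to 1, the number affected runs from 0 to about 30. The upper end is only a bound, because the age strata extend through 60-69 and 70-80 years.

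**4. Dose.** Section D gives about 60 mrem for the two scans together and cites 5000 mrem per year as the limit: 60 / 5000 = 1.2%, consistent with its statement that the share is below 3%.

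**The case against.** The strongest reply is that this is a small wording conflict with little practical risk.

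- **The instructions differ only at the margin.** For a post-menopausal woman both give the same result, and staff are likely to work from the visit schedule, which has the protective version. This stands as a mitigating point. It does not remove the conflict, because nothing says that the schedule prevails.
- **Reproductive information is available before the scan.** Medical history and physical exam are at visit 1, FSH at visit 2 and DXA at visit 3. But the protocol ties none of these to a decision on testing, and section D rules the test out regardless.
- **Harm needs more than menstruation.** It needs an undetected pregnancy at age 50 or over, which is unlikely, and the dose is low. This stands and limits the weight of the point. It supports restricting the test to menstruating women, as Table 3 does; it does not support a blanket statement that the test is unnecessary.
- **Many participants may already have been scanned.** The study timeline reports 37 enrolled at UCD and 31 at UW, 68 in all, when that text was written. A correction reaches only scans still to come. This also stands.
- **No analysis depends on it.** The primary outcome is the 400-m walk, and DXA body composition is exploratory. This is correct; the point concerns participant safety and consistency, not inference.

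**Conclusion.** The contradiction is real. Section D states a safety rule on a premise that the design does not secure, and the rule is the reverse of the scheduled procedure for the only women to whom that procedure applies. The text comparison rests on no assumption.

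The size is limited: about 30 women begin the intervention at the two DXA sites if 60 per site start and the 25% goal is met. The affected subgroup is of unknown size within that number, and the dose is 1.2% of the annual limit the protocol cites. There is no effect on power, estimation or any planned test. The sentence should still be corrected, because it is wrong as written and bears on radiation exposure.

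**What to change.** In section D, DXA, Risks, delete the statement that all women will be post-menopausal and that no test will be done. Replace it with the rule already in Table 3: a urine pregnancy test before each DXA scan in any woman who is still menstruating. In the same edit, say what follows a positive result, since the eligibility text now addresses pregnancy only for MRI/MRS.

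The alternative is to add post-menopausal status, with a stated definition, to the inclusion criteria for women and to remove the Table 3 row. That would make the section D sentence true but would narrow eligibility, so the first option is preferable.

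The first option costs protocol wording only. It adds no procedure beyond those already scheduled and changes neither the sample size nor the analysis.

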#### **Venipuncture:**

Risk: There is a small risk of local hematoma or infection associated with blood sampling.

Plans to minimize risk: The risks of hematoma and infection are minimized by having trained clinical personnel perform the procedures using sterile techniques.

Justification: Laboratory measures will be assessed pre-exercise to ensure that participants are safe for the intervention and will be utilized for the mitochondrial assessments. If the peripheral blood mitochondrial assessments are similar to that of the muscle biopsy, this would provide justification for avoiding muscle biopsy in the future.

#### **Fasting:**

Risk: There is a risk of hunger, and a small risk of dizziness, lightheadness, low blood sugar, and fatigue during fasting.

Plans to minimize risk: The risks of fasting will be minimized by encouraging participants to stay hydrated with water prior to the visit. For diabetics, diabetes medications will be held until the participant can have a snack.

Justification: Laboratory measures need to be obtained in the fasting state to minimize confounding and ensure validity.

**Stool collection (this will be optional):** There is risk of embarrassment or exposure to feces with sample collection.

Plans to minimize risk: Participants will be provided with instructions and a kit to safely collect the sample. This will be optional part of the study.

Justification: Due to differences in microbiome with exercise seen in our preliminary work, we will collect stool samples for microbiome and short chain fatty acids at baseline and week 16.

#### **Questionnaires:**

1. *Lee Fatigue Scale*. This validated, 7-item visual analog scale asks participants to rate, on a scale of 0 to 10, how much fatigue they are feeling “right now”. The *LFS* has been used to characterize fatigue profiles in PWH, allowing us to contextualize the effects seen with our exercise regimens within the larger population of PWH, and will help us to identify the fatigue phenotype most likely to benefit from HIIT or CME. Participants will be instructed to complete the *LFS* within 30 minutes of waking on 7 consecutive mornings and within 30 minutes before going to bed on the same 7 consecutive evenings. We have previously used longitudinal, daily assessments (including the *LFS*) to assess sleep quality and PA, and have honed a procedure whereby we obtain >95% data. We will use the recommended *LFS* scoring in which all items are averaged into morning and evening fatigue scores. The 7-day averages will be our **primary fatigue outcomes: total morning fatigue and total evening fatigue scores**.
2. PROMIS fatigue measure (an NIH common data element), a global measure of fatigue that will provide additional valuable data (e.g., sleep quality), allowing us to understand the clinical effects of our interventions on fatigue. Fatigue assessments will be completed every 4 weeks throughout the exercise and behavioral intervention by a research assistant blinded to the intervention arm.
3. *HIV Symptom Index*, a validated measure of 20 common HIV-related symptoms
4. *The Friendship Scale*, a validated 6-item measure of isolation.
5. Patient Health Questionnaire (PHQ)-9
6. Pittsburgh Sleep Quality Index
7. Epworth Sleepiness Scale
8. PROMIS Physical function
9. Brief Falls Assessment
10. Diet log: Self-reported food intake over 3 days will be collected between baseline visits #2 and 3 using the CTSC standardized collection form.
11. Microbiome Questionnaire
12. Demographics questionnaire
13. Monthly Health Status
14. LURN Symptom Index-10
15. Technology Acceptance Survey
16. Functional Activities questionnaire and Cognitive Failures questionnaire
17. Psychological mechanisms of adherence to exercise (measures described in Table above)
18. Ultrasound Feasibility & Acceptability Questionnaire
19. Connor Davidson Resilience Scale
20. Prior Intervention Exercise Questionnaire (UCD and UW Only)

**Risks** There is minimal risk associated with completing these questionnaires. If someone indicates extremely poor well-being on the well-being questionnaire, they may be referred to the emergency room or their provider, after discussion with the patient and assessment of any harm.

**Plans to minimize risk** Participants will be instructed to take breaks or skip questions on the surveys if they feel uncomfortable completing them.

**Benefit:** A better understanding of how exercise models impact symptoms and isolation in a population that disproportionately experiences high symptom burden will allow us to understand if we can improve these symptoms using nonpharmacological strategies. The ability to counsel patients about if, how much, and what type of exercise will reduce fatigue and other symptoms will improve the quality of life of people living with HIV.

## Cognitive Assessment

**Risk:** Participants may express distress or mental fatigue during/after engaging in the cognitive assessment.

**Plans to minimize risk:** Any potential distress that could be reported during cognitive testing will be mitigated by employing skilled cognitive testers who are trained to assure participants that the tests are designed so that no one can do well on all of the tests, and there will be a point at which everyone can no longer do well. We have also selected a brief 1 hour battery to reduce participant burden and mental fatigue. We will also offer the participant breaks if needed. Though

we will not provide feedback on performance (as tests are not conducted by clinical neuropsychologists), for participants who indicate questions or concerns on their performance we will recommend they follow-up with their healthcare provider.

Justification: Administration of these measures are needed to understand the potential cognitive benefits of exercise.

**One-on-one Interview.** First, we will pilot test an interview guide on 2-3 PWH at UW and UCD-AMC and revise it accordingly. A final guide will be used to direct subsequent interviews consistently at both sites. The interviews will take place in a secure, private location. Questions will address the participants' perceptions of exercise; experiences with HIIT, CME, or resistance training; the coaching intervention; and what they think will help them sustain PA over the long-term. Interviews will take ~ 30 minutes, be audio-recorded, and transcribed verbatim. [name] has over 15 years of experience designing, implementing, and analyzing data from qualitative studies and has successfully trained and managed qualitative data collectors across sites, obtaining high-quality data. The interviews will be conducted in a quiet, private clinic room or conference room. Additional interviews (optional) will be conducted among participants who opt not to enroll after initially contacting the team with interest, or who decide to withdraw from the study after enrollment.

Risk: The main risk with the discussion is confidentiality or discomfort by the participant in interacting one-on-one with the interviewer.

Plan to minimize risk: Participation within the interviews will be entirely voluntary. All data will be collected using unique patient identification codes. Participant interviews will be conducted by an investigator familiar with qualitative interviews. The conversation will focus on the exercise intervention and no personal questions that might make the participant feel uncomfortable.

Justification: The goal of the Aim 3 mixed-methods analysis to fully describe and compare the perceptions of HIIT, CME, and effect of the coaching intervention to enhance self-directed PA in PWH. The addition of qualitative methods will provide insight into the aspects of health and wellness that are most valued by persons who are aging with HIV infection. The addition of the qualitative interviews allow each participant the opportunity to share his/her personal experiences.

### **Text Messaging Intervention.**

Risk: Based on our previous work using daily electronic data collection, adverse events (AEs) due to text messaging are not expected, and no dangers to participants are expected beyond those that may be encountered in everyday life. As part of their standard medical care participants already receive many different messages about their adherence behavior that may be phrased in many different ways, with no standardization in message framing across providers. None of the tailored messages to be delivered in this study are considered any more risky or potentially harmful than other messages about adherence participants might receive during their standard medical care for HIV (where adherence is frequently a topic of discussion between clinicians and patients), and this study's messages have the advantage of being pre-validated by experts for appropriateness and factual accuracy. Therefore, the tailored messaging intervention itself is not expected to create any special risk that participants would not already encounter in the course of receiving typical medical services for HIV. Confidentiality is also a concern, and discussed below.

Plans to minimize risk: All data collected over the Internet from participants' smartphones will be completely de-identified and not traceable to the individual completing the survey; survey data transmitted over the Internet will be identified with a smartphone device ID that is not meaningful outside the context of this study, will be transmitted using a secure Internet connection (<https://>) via RedCap. These surveys will ask about fatigue and physical activity, and will not inquire about anything HIV related.

Expected Benefits. Participants may benefit from improved exercise adherence if the intervention is successful. The knowledge to be gained from this study is important for developing better tailored interventions that can be widely and cheaply delivered via smartphones to help people improve their adherence to exercise, treatment for HIV or other chronic diseases.

